#### Proposed Mechanism of Oxytocin In Prader-Willi Syndrome, Hyperphagia And Obesity

*Pathophysiology:* Dysfunction of the oxytocin (OXT) system is implicated in the pathophysiology of PWS. Oxytocin (OXT) is a nonapeptide synthesized in the paraventricular (PVN) and supraoptic nuclei (SON) of the hypothalamus. It is proposed to play a role in social recognition, pair bonding, anxiety, maternal behaviors, metabolism, food motivation and hyperphagia. OXT receptors are expressed in numerous brain regions including the amygdala, ventromedial hypothalamus, and the brainstem. The number and size of OXT neurons in the PVN is significantly reduced in PWS [29;45].

Animal Models: Faulty OXT signaling is also associated with obesity, which is a large issue in the PWS population. OXT's role in obesity has been studied in mouse models. For example, OXT supplementation is demonstrated to reduce food intake and body weight in a mouse model of diet-induced obesity [26;46]. Mice with haploinsufficiency of SIM1, a gene essential for the formation of the PVN, are characterized by hyperphagic obesity, similar to patients with PWS, and reduced OXT and melanocortin-4 receptors [46]. When OXT was administered to these mice, their food intake decreased and they lost weight in excess of what could be explained by decreased food intake alone [46]. Thus, peripheral administration of OXT has been shown to treat obesity by reducing food intake and visceral fat mass in a mouse model [26]. In addition, neuronal c-Fos expression, a marker for cell proliferation, differentiation and survival, increases in the NTS and AP in response to peripheral OXT. The nucleus of the solitary tract (NTS) and area postrema (AP) are hindbrain areas heavily involved in the processing of satiety signals.

In early studies of hypothalamic function, lesions of oxytocin containing hypothalamic nuclei were shown to result in an increase in food intake and body weight [81-84]. In the 1990s, several studies reported on the anorexigenic effects of central oxytocin. Low doses of oxytocin given intracerebroventricular (ICV) dose- dependently inhibited food intake in rats, increased

the latency to begin feeding and reduced meal duration in both hungry and satiated animals. These actions could also be blocked by oxytocin receptor antagonists [85;86]. Longer term central infusions of oxytocin were also reported to reduce body weight gain in rats given a high-fat diet. However, in contrast to oxytocin's acute effects, chronic oxytocin infusions did not alter total food intake or meal patterning, but instead appeared to stimulate lipid metabolism in adipose tissue [88]. This suggests that similar to the effect of LH/FSH in inducing puberty, a pulsatile release of oxytocin may be preferable than a chronic infusion administration. Additionally, both male and female oxytocin-knockout mice show an elevation in body weight and fat stores in adulthood, but as with oxytocin receptor-deficient mice, this is not due to an increase in food intake and is solely related to the lack of oxytocin receptors [87]. While there have been no published reports of humans that completely lack either oxytocin or its receptor, most likely due to the fact that the absence of oxytocin or its receptor is incompatible with successful reproduction, a partial deficiency in central oxytocin production has been associated with the development of obesity in humans in two documented conditions.

*Data from Studies in Humans:* As shown above, oxytocin and its role in obesity and food motivation have been repeatedly investigated at the animal model level, but in humans it has only been studied limitedly, despite many models that demonstrate its role in these processes. Fortunately, studies are currently underway to study the effect of oxytocin on food motivation in humans [78:NCT02276677]. Additionally, a recent study of healthy volunteers [79] showed that IN-OXT reduced snack intake by 25%; attenuated basal and postprandial levels of adrenocorticotropic hormone and cortisol; and curbed post-meal glucose elevation. Although data on oxytocin as a treatment for hyperphagia in humans is limited, one study in human subjects with PWS demonstrated that 45% of those on IN-OXT vs. 10% of those on placebo had reduced hunger and decreased food intake (OR = 7.85) after a single dose of 24 IU IN-OXT [47]

**Data from a Similar Disorder: Autism Spectrum Disorder (ASD):** In addition to PWS, OXT has also been implicated in the pathophysiology of ASD, and multiple clinical trials of IN-OXT in this population have been completed as a result. While trials have differed in age range, outcome measures, dose of OXT and some studies have yielded mixed results, in general over different age ranges and with different outcome measures, most findings suggest some improvement of repetitive behavior (especially lower order repetitive behaviors) and social cognition with IN-OXT in ASD. Abnormalities in the neural pathways for OXT contribute to the behavioral manifestations of ASD [41]. Treatment with intranasal oxytocin (IN-OXT) vs. placebo in ASD populations has resulted in improvement in repetitive behaviors and social information processing deficits that are characteristic of PWS, in particular improvement was observed in the lower order self-stimulatory behaviors [42-44].

A recent double-blind, placebo-controlled, parallel design pilot study of 24 IU BID IN-OXT vs. placebo in 19 adults with ASD showed significant improvement on measures of repetitive behaviors, social cognition and quality of life with IN-OXT when compared to placebo [44]. Safety data showed no serious adverse effects, with mild to moderate irritability, nasal congestion/allergy symptoms, headache and increased energy reported when the patient was taking IN-OXT. The study included women (3/19) and after evaluating distributions to assess the need for data transformations, no statistical evidence of distributional concerns were found, therefore, no transformations were made [44]. Previous studies have shown a reduction in repetitive behaviors and an increased ability to assign emotion to speech intonation with titrated intravenous oxytocin in adults with ASD [42, 43], in addition to improved empathic accuracy in healthy volunteers with high scores on the Autism Quotient scale with 24 IU of IN-OXT [41].

The safety and efficacy of IN-OXT has also been demonstrated in children and adolescents with ASD. Adolescents with ASD treated with open label IN-OXT with 2 month stepwise dosage increases (8, 16, 24 IU) showed improvement on communication and social interaction domains of the Autism Diagnostic Observation Schedule (ADOS) and trends in improvement on the social withdrawal scale of the Aberrant Behavior Checklist (ABC) and the delinquent behavior scale of the Child Behavior Checklist (CBCL). As in previous studies there were no serious adverse effects or impairments in short-term memory. This is one of the few studies demonstrating the safety of long term administration (6 months) of IN-OXT [54]. In a similar study, males aged 12 to 19 years with ASD or Asperger's Disorder received a single challenge of IN-OXT (18 IU or 24 IU) one week apart. IN-OXT was noted to improve performance on the Reading the Mind in the Eyes Test (RMET), with a highly significant effect on the easy items of the assessment [55]. As seen in prior studies there was no difference across sessions with regard to drug identification or in the number of reported side effects. Side effects from IN-OXT included feeling tired and relaxed, and sweating, while those with placebo also reported feeling tired and relaxed, in addition to headaches and coughing. A recent negative trial of IN-OXT in male children aged 7 to 16 years looked at the effect of a 24 IU or 12 IU dose over the course of 5 days combined with Parent-Child Interaction Therapy (PCIT). Although there was no separation between placebo and IN- OXT, minimal side effects were observed, further demonstrating the safety of IN-OXT younger populations [56].

**Previous Studies Of Intranasal Oxytocin In Prader-Willi Syndrome And Their Limitations:** The first study showed that a single low dose of 24 IU IN-OXT vs. placebo in 24 adult patients with PWS (16 female and 8 male) had significant effects on reducing disruptive behaviors using a clinician-rated behavior grid (d = 0.72), and on increasing trust. IN-OXT was determined to be safe and effective. Additionally, although not statistically significant, 45% of those on IN-OXT vs. 10% of those on placebo had reduced hunger and decreased food intake (OR = 7.85). However, this study only involved a single administration of IN-OXT and did not employ any standardized measure to monitor food intake or behavioral measures [47].

The second study [72] enrolled 30 subjects aged 12 - 30 years (20 males and 10 females) in an 18-week, randomized, double-blind, placebo-controlled crossover trial. 11 subjects received 24 IU IN-OXT BID (16 years and older) or 18 IU BID (13 - 15 years). 18 subjects received 40 IU BID (16 years and older) or 32 IU BID (1315 years). The study found little impact on any of its outcome measures (Developmental Behavior Checklist Monitor, Parent, Teacher, and Adult; Yale-Brown Obsessive Compulsive Scale; The [name] Hyperphagia questionnaire; Reading the Mind in the Eyes Test; Epworth Sleepiness Scale and the Movie Stills). However, there was an increase in the number of temper tantrums (p = 0.023) on the higher doses of IN-OXT (40 and 32 IU), which could have been due to increased binding of oxytocin to V1a receptors and have resulted in increased aggression. This could also be bias against finding improvement on other behavioral measures.

[name] recently completed a double-blind, placebo-controlled crossover study of IN-OXT vs. Pbo in 24 children with PWS. Children were randomized to receive 5 days of either IN-OXT followed by placebo, or vice versa, with a minimum 4-week washout between the treatment periods. All children were in the Phase 2b or Phase 3 nutritional phase. Results revealed that all scales factor improvement from Day 3 to Day 6 favored oxytocin over placebo. In addition, after 5 days of treatment with IN-OXT, there was a 2.5 point decrease (i.e., improvement) on the Hyperphagia Questionnaire compared to a 1.6 point decrease on placebo. In addition, improvements were demonstrated on IN-OXT versus placebo on the ABC Factors of lethargy/social withdrawal, inappropriate speech, irritability, stereotypical behaviors and hyperactivity (107). Another recent multicenter trial using the oxytocin analogue carbetocin

conducted by Ferring Pharmaceuticals also demonstrated improvement in hyperphagia in PWS using the Revised Hyperphagia Scale [Personal Communication, July 2015]. Aside from [name] study, these previous studies of IN-OXT treatment for PWS had several limitations which our group intends to improve upon. Firstly, the studies had small sample sizes. One was a pilot study and not powered to find statistically significant changes between treatment vs. placebo groups. Secondly, only a single dose of IN-OXT was administered and no standardized measures of hyperphagia or other outcomes were used. The second study found no separation between treatment with placebo vs. IN-OXT at high doses on the [name] Hyperphagia Questionnaire or other outcome measures. However, this study was small (n = 30) and the dose of IN-OXT may have been too high and have worked against detecting a signal for the reasons noted above. [name] study was also a small sample size and only dosed patients for 1-week with IN-OXT. Both she, and we, agree that further studies are necessary to look at long term effects of IN-OXT in PWS and to replicate findings at this dose of OXT.

In our currently blinded and ongoing pilot study of 16IU/day intranasal oxytocin vs. placebo, sponsored by the Foundation for Prader-Willi Research, we have enrolled 12 and randomized 9 patients with PWS over the last 3 months. Our recruitment goal is 24 patients. Thus far we have observed minimal adverse events, with only one, polyuria, possibly related to study drug. There have been no serious adverse events. We have also noted positive reports of hyperphagia, compulsivity and other behaviors (below).

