# SPECIFIC AIMS

#### OBJECTIVE

The primary objective of this Phase 2 trial is to compare the change from baseline to week 8 of the peptide intranasal oxytocin (IN-OXT) on changes in hyperphagia using the Hyperphagia Questionnaire-Clinical Trials (HQ-CT) in children and adolescents with PWS. We have obtained an IND for the use of IN-OXT for PWS (IND 121109) and have acquired both the IN-OXT and matching placebo (Manufactured by Novartis as Syntocinon - see letter and COA of Batch in appendix). We will also compare the effects of IN-OXT from baseline to week-8 on repetitive behaviors (RBS-R), weight, BMI and body composition, quality of life (WHOQOL, Caregiver Strain Questionnaire), salivary oxytocin concentration, and safety measures. Safety will be assessed with routine laboratory monitoring, physical exam, urine pregnancy test for menstruating females, and collection of vital signs. The Aberrant Behavior Checklist (ABC) will also be used as a safety measure for both suicidality (per FDA guidelines) and for adverse events (aggression/temper tantrums). This Phase 2 study is designed to generate preliminary data for future Phase 3 trials, and targets symptoms in this population that currently have no effective treatments. By treating these symptoms earlier in life in a pediatric PWS population we may maximize the treatment impact. This study supports the Orphan Product Divisions goal of identifying and promoting the development of treatments indicated for rare diseases or conditions. Our proposed treatment will target hyperphagia in subjects with PWS, a symptom for which there is currently no effective treatment.

This study will provide essential data that is needed for drug development and eventually drug approval.

We propose a three-year randomized, double-blind, placebo-controlled 8-week treatment trial of IN-OXT 16 IU/day in 50 subjects aged 5 to 17 years with PWS. To allow for dose optimization, we allow one downward titration to 12 IU if adverse events occur, and one upward titration to 24 IU at week 2 for lack of response on hyperphagia.

**Primary:** To compare IN-OXT vs. placebo on changes on the Hyperphagia Questionnaire-Clinical Trials (HQ-CT) from baseline to week 8 in children with PWS. We hypothesize that IN-OXT will be significantly superior to placebo in improving hyperphagia.

Secondary: To compare the change from baseline to week-8 of IN-OXT vs. placebo on:

- 1. Repetitive Behavior Scale-Revised (RBS-R).

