#### INNOVATION

This proposal shifts current drug development paradigms by selecting an orphan population, PWS, characterized by a known genetic and neuropathological mechanism (disruption of chromosome 15q11-q13 and a decreased of number and size of OXT-producing neurons in the PVN nuclei of the hypothalamus), and matching an available well tolerated treatment, IN-OXT, with a mechanism that targets the specific pathophysiology of the condition (faulty OXT signaling) to a specific homogeneous disorder. This novel drug development approach provides a substantially greater chance of detecting a drug vs. placebo signal in a more targeted and homogeneous population. This approach also targets the core deficits of PWS, disordered eating behaviors, which currently lack effective therapeutic interventions and contribute to disease burden and caregiver strain.

Our study will improve upon the design from the Einfeld study of IN-OXT [72] in six key parameters.

- 1. We have lowered the dose in response to the temper tantrums side effect observed, which we believe is a result of excess oxytocin binding to vasopressin receptors. Additionally, a lower dose may have a better impact on hyperphagia issues, as discussed above.
- 2. The Einfeld study [72] was a crossover design which raises issues regarding carryover and phase order effects, whereas our proposed study is a parallel design study.
- 3. The Einfeld study [72] sample size was much smaller (n=30). Our sample size is 50 subjects (25 vs 25).
- 4. Their population was older (ranging from 12 30 years), whereas in our proposed population (5 17), we have the ability to intervene at an earlier stage of the illness.
- 5. We only include subjects in PWS nutritional phase 2b or 3, in order to maximize severity of hyperphagia at baseline in our subjects. This will enhance our ability to detect a significant

reduction in hyperphagia for our active treatment vs placebo.

6. We will replicate the dose from the successful trial of [name] in childhood PWS, and from our current pilot trial of IN-OXT in patients with PWS.

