#### **PRIMARY OUTCOME:**

**Hyperphagia Questionnaire-Clinical Trials (HQ-CT)**: The Hyperphagia Questionnaire-Clinical Trials (HQ-CT) is the standard for assessing how potential therapies may impact hyperphagia in PWS clinical trials. It is a caregiver-rated assessment comprised of 9-items that measure and track the food seeking behaviors and drive for food that is associated with PWS. The HQ-CT is a modified version of the [name]-Hyperphagia Questionnaire (a well-established questionnaire), with changes based on industry and regulatory standards (e.g., Food and Drug Administration, 2009). These modifications included a reduced recall period, optimization of response scales, and limiting item content to observable behaviors that have the potential to change during the course of a clinical trial. Psychometric evaluation demonstrated the HQ-CT's reliability and validity, and the HQ-CT total score has demonstrated improvements in hyperphagia-related behavior between treatment groups in children with PWS. The HQ-CT will be administered at screening, baseline, and at all subsequent visits. In order to be eligible to participate in the trial, scores on the HQ-CT will need to be at least of moderate severity at both screening and baseline visits. It will take about 15 minutes to complete.

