were administered IN- OXT or placebo and salivary OXT was measured ten times over four consecutive hours. IN-OXT increased salivary OXT across the entire period. OXT rose dramatically 15 min after administration (from 6.9 pg/ml at baseline to 1265.4 pg/ml), reached plateau at 45—120 min (range = 131.6 and 105.3 pg/ml), and did not return to baseline by 4 h. The findings from these studies support target engagement in the CNS and refute the idea that salivary elevation results solely from movement of mucus from the nasal cavities back into the mouth.

We believe that plasma OXT levels are of less importance, as central and clinical effects do not reflect plasma PK levels, but that salivary OXT levels may be more closely correlated with CNS effects. We do not expect our one hour post-dose measurements to be affected by IN-OXT residue in the nasal cavity. As stated above, Gordon et al. [73] demonstrated salivary levels of OXT 30 minutes post-dose were strongly correlated with changes in brain activity and van IJzendoorn et al [99] demonstrated that salivary OXT levels peak 1 hour post- dose and a dose of 16 IU was correlated with higher salivary OXT levels than a 24 IU dose. Salivary concentrations are being measured at weeks 4 and 8 to determine if salivary OXT concentrations accumulate over time with chronic treatment of IN-OXT and to determine if the levels correlate with changes in clinical symptoms. We will measure both group and individual differences in salivary OXT concentration in addition to correlating individual salivary OXT concentrations at day 1 and weeks 4 and 8 with changes on the [name] Hyperphagia Questionnaire. We also believe that salivary OXT concentration measurements will induce less discomfort than plasma measurement for the children enrolled in the study. In sum, while levels of salivary oxytocin remain elevated for up to 7 hours, the standard and maximum levels observed in prior studies was observed at the 1 hour post-treatment measurement.

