#### **Detailed Description of Analyses**

**Primary Analyses**: Analyses for Specific Aim (1): To compare IN-OXT vs. placebo with respect to improvement in the hyperphagia severity in children with PWS via improvement in scores on the Hyperphagia Questionnaire-Clinical Trials.

The primary analysis will evaluate the hypothesis that IN-OXT will decrease hyperphagia vs. placebo.

- 1. Response to treatment will be assessed in two ways:
  - a. The effects of IN-OXT on hyperphagia will be analyzed using an intent-totreat approach with the two-sample T-test or Wilcoxon rank sum tests to compare treatment groups at specific visits as well as linear mixed effects models to analyze the repeated measures and changes over time.
  - b. The proportion of responders in each treatment group will also be compared. Response will be defined as a 30% or greater decrease in food-seeking and eating behaviors from baseline on the Hyperphagia Questionnaire-Clinical Trials. Dropouts for clinical reasons will be coded as non- responders. Differences in the proportion of responders in each treatment group will be evaluated using the chi-square test and time to response will be assessed using survival analytic techniques.
  - c. All tests will be two-tailed with an alpha level of 0.05.

**Secondary Analyses:** Analyses for Specific Aims (2) through (8): To compare IN-OXT vs. placebo in children with PWS on change in:(2) Repetitive behaviors via scores on the Repetitive Behavior Scale – Revised (RBS-R) and Montefiore-Einstein Rigidity Scale-Revised (MERS-PWS)(3) Weight and body composition via impedance analysis. (4) Quality of Life Measures on the World Health Organization Quality of Life Scale (WHOQOL)(5) Clinical Global Impression Scale (CGI-I) (6) Salivary Oxytocin Concentration (7) Safety Analyses

IN-OXT and placebo groups will be compared to the above secondary measures will be analyzed using methods similar to those outlined above. Associations between outcome measures at a specific time point will be analyzed with the Spearman rank or Pearson correlation coefficient.

- 1. Secondary Aim (1) Repetitive Behaviors
  - *a.* The effects of treatment on frequency and severity of repetitive behaviors will be assessed by fitting linear mixed effects models to the data on the RBS-R scores. We hypothesize that IN- OXT will significantly reduce repetitive behaviors from baseline to endpoint compared to Placebo.

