**Power Analysis: Sample size justification:** The target sample size for this Phase 2 trial is 25 patients per treatment group. The power for the study has been calculated to generate a detectable signal with the sample size of 50 subjects. With this sample size, the study will have 80% power to detect a minimum effect size of d= 0.8 standard deviations in the outcome measures between groups using a two-sample T-test and a two sided Type I error rate of 5%. The study is powered based on a conservative estimate from a heterogeneous population. We expect that in this homogeneous PWS population selected to match study drug to underlying mechanism, the true power will exceed the conservative estimate. This minimum detectable difference is smaller than the treatment effects observed in our previous studies of IN-OXT in adults with ASD, which demonstrated an effect size of d=1.2 on a social cognition measure (RMET) [3], and an effect size of d = 0.84 on a quality of life measure (WHOQOL) [3]. In addition, our previous study of a V1a antagonist in adults with ASD demonstrated an effect size of d=0.8 on a social cognition measure (ASR Lust) [80], and an effect size of d = 0.8 on an Eye Tracking measure (Biological Motion Preference) [90]. The above effect sizes observed in our pilot data were based on a heterogeneous sample of ASD patients characterized by over 100 known different genetic contributing factors. In the proposed trial, both males and females will be included, and any heterogeneity in outcomes due to gender may attenuate overall treatment differences. However, by selecting an orphan population (PWS) with a single unique genetic contribution, and selecting a treatment that matches the known molecular mechanism (IN-OXT), we expect that the treatment effects in this study will nevertheless be greater than the effects observed in earlier studies.

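### The week-8 HQ-CT comparison tests a flexible regimen starting at 16 IU/day; it does not isolate the 16 IU/day dose that the protocol says it replicates

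*Combined protocol and SAP*

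**What the plan says.** **Rationale.** The Objective and the Background and Significance section both label the study a trial of 16 IU/day. Under Previous Studies Of Intranasal Oxytocin In Prader-Willi Syndrome And Their Limitations, the stated need is that "further studies are necessary to look at long term effects of IN-OXT in PWS and to replicate findings at this dose of OXT". The section on low-dose evidence again presents the dose as a replication, and item 6 under Innovation opens with "We will replicate the dose from the successful trial of" an earlier paediatric study.

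**Dosing.** The Objective permits "one upward titration to 24 IU at week 2 for lack of response on hyperphagia". The Titration Schedule makes this optional. It requires that the study clinician, consulting the principal investigator, records no hyperphagia response (yes or no) and that there are no adverse events. A reduction to 12 IU/day is available for adverse events thought likely to be drug-related, with no fixed week.

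**Analysis.** The primary aim compares IN-OXT with placebo on HQ-CT change to week 8, and the Statistical Analyses section keeps children in their assigned arm. Under Primary Outcome, "The HQ-CT will be administered at screening, baseline, and at all subsequent visits"; the schedule of events includes week 2. Detailed Description of Analyses uses two-sample tests "to compare treatment groups at specific visits as well as linear mixed effects models". Week 2 is not named there, and the only visit given as an example under Summary of Analytic Approach is 8 weeks. The only dose-related analysis is exploratory and concerns weight-based dose.

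**The concern.** A reader who takes the rationale at face value will expect the primary result to say whether 16 IU/day works over eight weeks. After week 2, however, some of the active arm may be on 24 IU/day, and they get there because they were judged not to have responded. A positive week-8 result might owe something to the raise. A null result could not be held squarely against 16 IU/day.

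The documents do separate the two doses on one measure: they report that "a dose of 16 IU was correlated with higher salivary OXT levels than a 24 IU dose". That concerns salivary concentration, not hyperphagia, so it shows only that the protocol does not treat the doses as interchangeable in every respect.

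At stake is how the trial will be cited. It could be read as replicating, or failing to replicate, the 16 IU/day finding when its primary analysis estimates something else. The comparison closest to that finding would remain unlabelled.

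**Working it through.** **1. The plan's own power figure.** Inputs: 25 per group and "80% power to detect a minimum effect size of d= 0.8 standard deviations in the outcome measures between groups" (Power Analysis); "All tests will be two-tailed with an alpha level of 0.05" (Detailed Description of Analyses).

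- Normal approximation: power = Φ(d√(n/2) − 1.96) = Φ(0.8 × √12.5 − 1.96) = Φ(0.868) = 80.7%.
- Exact noncentral t, 48 df: 79.1%.

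The stated 80% is reproduced. At week 8 it belongs to the contrast between assigned arms, that is, to the regimen.

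**2. What week 8 estimates.** In SD units of HQ-CT improvement, and leaving aside reductions to 12 IU/day (which would add a similar term):

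week-8 effect = (effect had nobody been raised) + p × g

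Here p is the share of the active arm raised to 24 IU/day and g is the mean extra improvement (or loss, if negative) that the raise causes in those children. The documents give neither, so both are assumptions. Setting the week-8 effect at 0.8, the effect had nobody been raised is 0.8 − p × g:

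| p (children of 25) | g = −0.8 | g = 0 | g = 0.8 | g = 1.6 |
|---|---|---|---|---|
| 10% (2.5) | 0.88 | 0.80 | 0.72 | 0.64 |
| 25% (6.25) | 1.00 | 0.80 | 0.60 | 0.40 |
| 50% (12.5) | 1.20 | 0.80 | 0.40 | 0.00 |

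If few are raised, week 8 approximates 16 IU/day. If half are raised, the same observed result fits anything from no 16 IU effect to a larger one than was observed.

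**3. Whether grouping by dose received helps.** It does not. Children still on 16 IU/day after week 2 would include responders, non-responders who had any adverse event, and non-responders whom the clinician chose not to raise. Membership depends on response, tolerability and judgement after randomisation, so neither this group nor its placebo counterpart is a randomised group. The responder, time-to-response and mixed-model analyses also span doses after week 2.

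**4. What week 2 offers.** No raise is allowed before week 2, HQ-CT is scheduled then in both arms, and the visit precedes the rule that discontinues children not on full dose by week four. An HQ-CT rated before the titration decision therefore compares randomised groups on assignment to start at 16 IU/day, apart from any early reduction for adverse events.

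Precision with 25 per arm: 95% CI half-width = 2.011 × √(2/25) = 0.57 SD. Exact power is:

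| d | 0.8 | 0.6 | 0.5 | 0.4 |
|---|---|---|---|---|
| power | 79.1% | 54.7% | 41.0% | 28.3% |

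The short crossover trial described under Previous Studies reported falls of 2.5 and 1.6 points, a difference of 0.9, after five days. No SD is given. For 0.9 points to equal d = 0.8 the SD would have to be 0.9/0.8 = 1.125. At assumed SDs of 2, 3 and 4 points, power for 0.9 points is 34.5%, 18.0% and 12.2%.

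**5. Spray counts.** Research Strategy And Feasibility gives 4 IU per spray and 6 sprays for 24 IU/day (6 × 4 = 24). The Titration Schedule gives 4 sprays for 24 IU/day, but 4 × 4 = 16. Read literally, the latter is no change of dose. The two must be reconciled before exposure can be described.

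**The case against.** The strongest reply is that no aim or hypothesis names 16 IU/day. The trial tests IN-OXT against placebo, and that remains a valid randomised comparison. The titration is disclosed beside the 16 IU/day label as dose optimisation, and Research Strategy and Study Intervention call 16 IU/day the initial dose. The earlier negative trial gave 18 to 40 IU twice daily, or 36 to 80 IU/day, so the whole 12 to 24 IU/day range lies below it. A positive week-8 result would therefore still bear on whether lower doses work. Week 2 is also not ignored: it falls under the generic visit-level tests and enters the mixed model.

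All of this stands and limits the point. None of it supplies a 16 IU/day estimate or labels one.

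A reader might infer three stronger things, and the documents support none of them:

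- **That the primary analysis is invalid.** It is valid for the flexible regimen.
- **That every week-2 non-responder moves to 24 IU/day, leaving only early responders on 16 IU/day.** The raise is optional and barred where there are adverse events.
- **That week 2 could settle the replication question.** The stated need includes long-term effects, which two weeks cannot address, and d = 0.8 is a favourable assumption for its power.

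**Conclusion.** The point holds as a mismatch between the 16 IU/day rationale and what the primary analysis estimates. It is not a flaw in the test of IN-OXT against placebo. The size of the mismatch is p × g, and both terms are unknown. For a week-8 effect of 0.8 SD and g between −0.8 and 1.6, the 16 IU effect could lie between 0.64 and 0.88 if 10% are raised, 0.4 and 1.0 if 25% are, and 0 and 1.2 if 50% are. These ranges illustrate the dependence and are not predictions. A flat statement that week 8 says nothing about 16 IU/day would go too far, because with few raised it says a good deal.

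The change is worth making because it is cheap and because week 2 is the last randomised comparison before any upward titration. It should be read as an estimate with an interval, not as a deciding test.

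**What to change.** 1. Wherever the Objective, Background and Significance, Previous Studies, the low-dose evidence section and Innovation item 6 present the trial as one of 16 IU/day or as a replication of that dose, state that the week-8 result is the effect of a flexible regimen starting at 16 IU/day. Report by arm how many children had their dose changed, and the dose at week 8.
2. In Detailed Description of Analyses, pre-specify the week-2 HQ-CT difference between arms, in all randomised children and rated before the titration decision, as a secondary estimate of assignment to start at 16 IU/day. Give it with a 95% CI beside the week-8 result.
3. Reconcile the spray count for 24 IU/day between the Titration Schedule and Research Strategy And Feasibility.

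The cost is protocol and SAP wording; week-2 HQ-CT is already scheduled. The limits should be stated with the estimate: it covers two weeks only, cannot answer the long-term question, may include early reductions for adverse events, and is imprecise below d = 0.8. No change to dosing is proposed.
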